### **Study design:**

The proposed study is pilot/feasibility study, in which the effectiveness of topical oxygen (100%) administered four days per week, for 16 weeks, for the treatment of diabetic foot ulcer (DFU) or chronic wound will be compared with standard of care (SoC) treatment.

- Subjects will be randomized into one of the two patient groups: **Group 1** will only receive standard of care (SoC) treatment.

#### **STANDARD OF CARE THERAPY (SoC):**

At the Comprehensive Wound Center, standard of wound care adheres to Clinical Practice Guideline, based on Wound Healing Society recommendations. Standard of care procedures (SoC) are intended to optimize conditions for wound healing and to ensure that a subject's safety is not compromised by taking part in this clinical study. The following standard of care procedures are routinely applied to patients at the Wound Center regardless of the group allocation across the entire duration of his or her participation in the clinical study.

- Wound cleaning and irrigation with normal saline
- Wound Dressings changes (examples below):
  - Non-adhering contact layer: open-mesh primary wound contact layer comprised of cellulose

- acetate coated with a soft tack silicone.
- Non-Adhering gauze dressing: gauze is made of knitted cellulose acetate fabric mesh that is coated with petrolatum emulsion.
- Off-loading:
  - Total contact casts (TCC) represent the best offloading practices.
  - Total contact casts will be changed on a weekly basis, and as needed for large exudative type wounds, twice weekly. An alginate or foam dressing will be incorporated over the foot ulcer prior to application.
  - If the subject is unable to use TCC or has discontinued using TCC for any reason, the subject will be offloaded with a removable cast walker. The reason for not using or discontinuing use of TCC will be recorded.
- If infection is suspected, appropriate therapy should be initiated according to the local therapy guidelines.
- **Group 2** will receive standard of care treatment plus Topical Oxygen Therapy. The provider will continue routine Standard of Care (SOC) that began prior to Topical Oxygen (TO) Therapy. Any changes in SOC will be based upon clinical practice guidelines and at the providers' discretion. [SOC changes will be documented by the research team to be considered during data analysis.]
  - The therapy will be applied in an identical manner utilizing the Topical Oxygen (TO) delivery device (FDA class II device) manufactured by GWR Medical Inc., and will be connected to an oxygen generator/concentrator. The devices maintain a constant pressure of 1.03 ATM which is just slightly above atmospheric pressure and much less than the typical 2.5 ATM used in hyperbaric oxygen (HBO) chambers.
  - All TO treatments will be provided in a home care or extended care (i.e. nursing home) setting.
  - They will be inflated with 100% FIO2 in the TO group.

Five study visits are planned as a part of this study (Table -1).

**Table-1: Study Timeline**

Week(s)	0 (Visit 1)	1-3	4 (Visit 2) (+/-2 weeks)	5-7	8 (Visit 3) (+/-2 weeks)	9-11	12 (Visit 4) (+/-2 weeks)	13-15	16 (Visit 5) (+/-2 weeks)
Study Visit	✓		✓		✓		✓		✓
Digital Imaging	✓		✓		✓		✓		✓
Topical oxygen or SoC treatment administered at home	✓	✓	✓	✓	✓	✓	✓	✓	✓

**Study Population:** 40 chronic wound patients with diabetes will be recruited based on study inclusion and exclusion criteria by the research personnel. Patients will be randomized into one of the 2 patient groups: the topical oxygen group and the other half randomized into the comparison group.

A proportionate stratified random permuted block design will be used to generate random assignments to the two groups. The stratification will be based on the proportion of patients expected to be seen at a wound center with Wagner grade 1, 2, or 3. This method will ensure balance across the groups and strata and will also account for the difference in the severity over the course of the study period. The biostatistician at the Center for Outcomes Research in Surgery will prepare the master randomization assignment list. The clinical research coordinator will administer randomization using REDCap.

**Blinding.** This is an open label trial. To reduce bias, the personnel involved in evaluating study outcomes will be blinded to treatment group. The standard of care will be provided by their providers at CWC as part of their routine wound care and will not be blinded to treatment group.

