#### **Inclusion Criteria:**

- 1) Age  $\geq$ 18 years
- 2) Able to give informed consent, willing and able to complete study requirements.
- 3) Diabetic
- 4) Chronic wound **OR** Foot Ulcer:
  - a. Ulcer present by history  $\geq$ 4 weeks at time of enrollment

- b. Compliant with standard wound care regimen
- c. If foot wound, Wagner grade 1 or 2, **–OR–** Wagner grade 3
- d. Ulcer size :  $0.6 \text{ cm}^2$  to  $20 \text{ cm}^2$  and has not decreased in size by more than 30% in previous 2 weeks of the enrollment visit
- 5) Adequate circulatory status, as evidenced by any of the following (for target wound located below the knee):
  - a. Ankle Brachial Index (ABI)  $\geq 0.7$  -  $\leq 1.20$
  - b. If ABI non-compressible (ABI  $> 1.2$ ), then toe brachial Index (TBI)  $> 0.5$
  - c. SPP  $> 30 \text{ mmHg}$
  - d. TcOM  $> 30 \text{ mmHg}$
- 6) At least 4 weeks since revascularization procedure, if one has been performed
- 7) Able to complete Topical Oxygen Therapy 4 days/week for 16 weeks (must be able to remove existing wound dressing and apply TO2 Boot/ treatment, and then re-dress wound)

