##### **a. Initial Visit (Visit 1):**

1. The research staff will screen the patients' medical chart for inclusion and exclusion criteria (current CWC patients only).
2. The informed consent will be presented to the patient.
  - Confirmation of the study eligibility including the inclusion and exclusion criteria will be reviewed with the patient; Subjects who self-refer from outside of the IU system will be asked to sign a release of information form so records can be requested &

reviewed for inclusion/ exclusion criteria.

An ankle brachial index will be completed for subjects with below the knee wounds if not already completed per standard of care since wound onset to confirm study eligibility. Those with an ABI < 0.7 or > 1.2 will be excluded and no further study activities will be completed. These subjects will not be enrolled.

3. Included in this initial (baseline) visit will be:
  - Randomization into one of the 2 study groups per Randomization plan
  - Medical history review
  - Concomitant medication review
  - Wound history review (onset, location, etiology, size, infection status, previous treatments)
  - Digital imaging of ulcer input to Wound Matrix™
    - The digital images will be input into a secure web based wound management program, Wound Matrix™ (Wound Matrix, Inc., Chadds Ford, PA, USA) that will be used for planimetric analysis of wound size.
  - Patient will be asked to complete the quality of life questionnaire (SF-36)
  - Point-of-care testing Hemoglobin A1c will be obtained for all subjects who have not had one completed as SoC within 90 days prior to this visit
4. Patients will also be provided with teaching regarding diabetes, footwear, and wound care.
5. Patients will be given a diary (see example at the end) to log their treatment

**b. 4, 8, 12 Week Visit (+/- 2 weeks):** Subjects will be asked to return to the CWC to complete repeat digital imaging of the ulcer. For those who are receiving wound care at the CWC, as much as possible, study visits will be scheduled in conjunction with regularly scheduled wound care appointments. Additionally, for those randomized to the topical oxygen treatment group, all follow-up visits will be calculated from the first day of topical oxygen therapy. The following will be completed during the study visit:

- Digital imaging of the ulcer to measure the response to therapy
- Any wound or health complications will be noted
- Medication review
- Collection of previous diary

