**c. At Home Treatments (4 consecutive days per week, treatment group only):**

1. A trained, approved study personnel will first attend the subjects' home

or extended care facility to provide the supplies, instruct and give support on how to use the TO device (performed solely for research purposes only)

- The approved personnel will teach the subject how to use the TO device and instruct the subject to complete this treatment 4 consecutive days a week, followed by 3 days of no treatment.
- The treatment will begin with the study personnel during the first home care (on site) visit:
  - The 90 minute therapy includes the removal of the ulcer dressing, the ulcer is cleansed/ moistened and the extremity is inserted into an FDA cleared single use oxygen delivery device (GWR Medical, Inc. Chadds Ford, PA).
  - If necessary, a band around the wound is prepared for fixation of the Topical Oxygen device by shaving the limb circumferentially over approximately a 10cm band (done at initial treatment and as needed subsequently).
  - After the 90 minutes, the single use device will be removed and disposed of.
    - Wounds will be treated with standard care at the physician's discretion and diabetic foot ulcers (DFUs) will be administered with a standardized offloading boot to distribute pressure across the entire surface of the foot, specifically removing pressure from the ulcer site per SoC (a non-antimicrobial boot).

2. Trained study personnel will be assigned for the subject, who will receive at home support for the treatment. The study personnel will make weekly phone calls to the subject to check on progress with TO therapy; personnel may go to the subject's home/ care facility on as as-needed basis if the subject is having difficulty with the treatment.
3. Subjects will be given a data collection log (diary) to document the date, time and that the treatment was completed. This will be checked at each study visit and will be collected at their next follow-up visit for compliance.
4. Treatments will continue until the ulcer has closed, an amputation (above or below knee) has been performed, the ulcer's healing has stalled (defined that the size of the wound is unchanged or increased in size in the past 2 visits) or 16 weeks of therapy has been completed.

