d. **SoC group only-** Patients will receive Standard of Care for their wound per the study physician's discretion. There will be no at home treatments for this study population but they will be asked to return for follow-up visits at 4, 8, 12, and 16 weeks following their baseline visit.

1. Subjects will be given a data collection log (diary) to document information about the SoC including wound dressing intact, offloading boot being used (for DFU's), the date, and the subject's initials. This will be checked at each study visit and will be collected at their next follow-up visit for compliance.
2. SoC will continue until the ulcer has closed, an amputation (above or below knee) has been performed, or the ulcer's healing has stalled (defined that the size of the wound is unchanged or increased in size in the past 2 visits).

All wounds for both groups will be treated with standard care and will be administered with a standardized offloading boot that distributes the pressure across the entire surface of the foot, specifically removing pressure from the ulcer site will be utilized (a non-antimicrobial boot). Offloading boots are standard of care for these wounds and will not be provided by the study.

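### Randomization is stratified by Wagner grade and the objective is risk-adjusted, but no planned comparison uses the strata or states a use for the baseline SF-36

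*Combined protocol and SAP*

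**What the plan says.** **Randomization.** The Study Population text after Table 1 plans permuted blocks within strata and says that "stratification will be based on the proportion of patients expected to be seen at a wound center with Wagner grade 1, 2, or 3". It adds that the method "will also account for the difference in the severity over the course of the study period". No other stratification factor is named.

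**Objective.** The aim is stated as risk-adjusted outcomes, with healing, amputations, complications and cost in parentheses. The secondary outcomes, SF-36 among them, are set against the baseline visit. The study is a pilot meant to supply inputs for a larger trial. Eleven subjects are already enrolled and 29 are to follow.

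**Analysis.** The Statistical analysis section gives descriptive summaries, cumulative incidence of healing per group, a bivariate logistic regression for healing, and two-group tests for secondary outcomes (t or Mann-Whitney for SF-36 and cost). It names no stratum, covariate or baseline score. The Sample size section uses a one-sided Fisher's exact test at 0.05.

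**Data available.** SF-36 is taken at baseline and at Week 16. Wound location is part of the baseline wound history.

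**Eligible wounds.** Under Study design, topical oxygen "for the treatment of diabetic foot ulcer (DFU) or chronic wound will be compared with standard of care". Inclusion criterion 4c begins "If foot wound, Wagner grade 1 or 2", with grade 3 as the alternative, so a grade is asked of foot wounds only. The circulation criterion applies "for target wound located below the knee", and the Initial Visit section likewise says "An ankle brachial index will be completed for subjects with below the knee wounds".

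**The concern.** Stratifying the randomization balances severity by design. It does not adjust any estimate. A plan that states a risk-adjusted objective, randomizes within severity strata and then analyzes everything bivariately does not deliver what it announces. The only analysis-stage promise is that changes in standard of care will be taken into account; those changes occur after baseline, and no method is given.

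The SF-36 has a related gap. The Objective suggests change from baseline, but the analysis section does not say whether the t-test is applied to the Week 16 score or to the change. The choice affects power, and neither is the most efficient use of two measurements.

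What is at stake is the quality of the inputs for the larger trial (a stratum-adjusted odds ratio and a baseline-adjusted SF-36 effect), plus some power. Validity is not at stake.

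**Working it through.** **1. The plan's own figure.** Inputs: 20 per arm, 50% vs 10%, one-sided Fisher at 0.05 (Sample size section). Summing Bin(a; 20, 0.5) × Bin(b; 20, 0.1) over all 21 × 21 tables with Fisher p ≤ 0.05 gives 83.7%. The stated power of at least 80% reproduces.

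**2. Validity of ignoring the strata.** Simulation under the null: assumed 7/7/6 per arm in three strata, one-sided 5%, 40,000 runs, and standard-of-care (SoC) healing patterns of 30/30/30, 50/30/10, 70/30/5 and 15/10/3%. The rejection rate of the unstratified test was 2.3 to 5.2%. There is no material inflation, and the test is conservative when strata are strongly prognostic.

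**3. Healing with and without strata.** The documents give no stratum shares or rates, so these are assumptions: 7/7/4/2 per arm for Wagner 1 / 2 / 3 / non-foot, and SoC healing of 10% in non-foot wounds. SoC rates in grades 1 / 2 / 3 are 20/5/2% (near plan), 22/3/1% (steep), 15/8/5% (weak) or 10% throughout (not prognostic).

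Check of the near-plan case: SoC = (7×0.20 + 7×0.05 + 4×0.02 + 2×0.10)/20 = 2.03/20 = 10.2%. With an odds ratio (OR) of 12 the treated rates are 75.0, 38.7, 19.7 and 57.1%, averaging 49.4%.

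Two pairs of tests were enumerated exactly over all stratum totals m_k (n_k per arm, a_k treated subjects healed):
- Mantel-Haenszel (MH): z = (Σa_k − Σm_k/2)/√ΣV_k, with V_k = n_k²·m_k(2n_k − m_k)/[(2n_k)²(2n_k − 1)], rejecting above 1.645; compared with the same test on the pooled table.
- Exact: P(Σa_k ≥ observed | all m_k, OR = 1), from convolved hypergeometric distributions, rejecting at ≤ 0.05; compared with Fisher on the pooled table.

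| Scenario | OR | MH stratified vs pooled | Exact stratified vs Fisher |
|---|---|---|---|
| Near plan | 12 | 92.7 vs 91.3% | 85.7 vs 84.1% |
| Near plan | 6 | 67.5 vs 63.9% | 51.8 vs 49.1% |
| Steep | 12 | 89.4 vs 85.8% | 79.7 vs 75.1% |
| Steep | 6 | 63.4 vs 56.5% | 46.5 vs 40.7% |
| Weak | 9 | 89.1 vs 88.9% | 80.9 vs 81.0% |
| Weak | 6 | 72.3 vs 71.8% | 58.5 vs 58.6% |
| Not prognostic | 9 | 90.2 vs 90.7% | 83.0 vs 83.7% |
| Not prognostic | 6 | 74.0 vs 74.3% | 60.9 vs 61.9% |

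Only the difference within a column is the effect of stratifying. The gap between columns is choice of test and is not a benefit.

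**4. SF-36.** Assumptions: true difference 0.8 SD, 20 complete per arm, two-sided 5%, baseline correlation r. Power comes from the noncentral t with noncentrality 0.8/√(v×2/20). For the Week 16 score v = 1 (df 38). For change v = 2(1 − r) (df 38). For ANCOVA v = (1 − r²)(1 + 1/36) (df 37). Example at r = 0.5: ANCOVA v = 0.75 × 1.0278 = 0.771, noncentrality 2.88, power 80%.

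| r | ANCOVA | Change | Week 16 score |
|---|---|---|---|
| 0.3 | 72% | 55% | 69% |
| 0.5 | 80% | 69% | 69% |
| 0.7 | 93% | 89% | 69% |

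At r = 0, ANCOVA gives 68%, a loss of 1 point against the Week 16 score.

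**5. Non-foot wounds among those enrolled.** If a share s of eligible wounds is not on the foot, the chance that at least one of the 11 enrolled subjects has such a wound is 1 − (1 − s)^11. That is 43 / 69 / 91% at s = 5 / 10 / 20%. The share is not given. A stratified analysis therefore needs a category for these wounds, whatever list they were randomized from.

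**The case against.** **The unadjusted analysis is sound, and the gain is small.** Both are true. Near the planned rates the gain is 1 to 2 points. Larger gains need steep strata or an effect smaller than planned, and the Sample size section says that detecting a difference is not the main objective. This keeps the point minor. It does not close the gap between the stated objective and the analysis.

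**Replacing the planned test would be preference.** This stands. The planned logistic regression and Fisher's test should remain, and the stratified comparison should be added to them.

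**A pilot this small cannot support adjustment.** This stands in part. In simulated near-plan trials the MH odds ratio was zero or infinite in 13 to 18%, so the point estimate alone is not enough. An exact stratified test with an interval is still feasible.

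**Stronger readings.** A reader might infer that the plan discards the baseline SF-36. The documents do not show that: the Objective sets secondary outcomes against baseline, and a t-test on change would fit. What can be said is that no use is stated.

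A reader might also infer that the randomization fails for non-foot wounds, which have no named stratum. The biostatistician's master list may cover them, and it is not in the documents. Such wounds may also be few. Weekly compression dressings are excluded, treatment uses a boot into which the extremity is placed, and the text after the SoC group procedures says "All wounds for both groups will be treated with standard care and will be administered with a standardized offloading boot". Against that, the At Home Treatments section singles out foot ulcers: "diabetic foot ulcers (DFUs) will be administered with a standardized offloading boot". Eligible non-foot wounds are therefore not ruled out, but this is a wording gap of unknown harm.

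**Conclusion.** The point holds as a minor one. No planned comparison uses the Wagner strata, and no use of the baseline SF-36 is stated, although the objective is risk-adjusted and the data are already collected. The documents do not support calling the analysis invalid or biased.

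For healing, stratifying is worth about 1 to 2 points of power near the plan, about 3 to 7 points if grade is strongly prognostic or the effect is smaller, and close to nothing if grade is weakly prognostic. If grade is not prognostic it costs 0.3 to 1.0 points. For the SF-36, ANCOVA matches or beats both simpler analyses except when r is near zero, where it costs about 1 point.

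The reading of the text is firm. The sizes rest on assumed stratum shares, healing rates, SF-36 effect, correlation and complete follow-up, none of which the documents give.

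**What to change.** 1. **Statistical analysis, healing.** Keep the planned unadjusted analysis and Fisher's exact test. Add: *Healing at 16 weeks will also be compared by an exact conditional test stratified by baseline Wagner 1 / 2 / 3 / non-foot, one-sided 0.05. The common odds ratio will be reported with its exact conditional two-sided 90% interval (or one-sided 95% lower bound). All 40 subjects are classified by baseline wound location and grade.* The interval level must match the test. An uncorrected one-sided 0.05 MH test paired with a two-sided 95% exact interval would disagree in about 15% of near-plan trials, and in 28% at OR 6.
2. **Statistical analysis, SF-36.** Add: *Week 16 SF-36 scores will be compared by ANCOVA on the baseline score.*
3. **Objective.** Limit the risk-adjusted wording to the outcomes actually adjusted; amputations, complications and cost stay unadjusted.
4. **Study Population (clarification only).** State which list an eligible non-foot wound is randomized from.

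**Cost.** A few sentences and no new data, provided that location, grade and baseline SF-36 exist for the 11 subjects enrolled earlier. The downsides are the small power losses above and a common odds ratio that may be zero or infinite, so it must always be reported with its interval.

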#### **Inclusion Criteria:**

- 1) Age  $\geq$ 18 years
- 2) Able to give informed consent, willing and able to complete study requirements.
- 3) Diabetic
- 4) Chronic wound **OR** Foot Ulcer:
  - a. Ulcer present by history  $\geq$ 4 weeks at time of enrollment

- b. Compliant with standard wound care regimen
- c. If foot wound, Wagner grade 1 or 2, **–OR–** Wagner grade 3
- d. Ulcer size :  $0.6 \text{ cm}^2$  to  $20 \text{ cm}^2$  and has not decreased in size by more than 30% in previous 2 weeks of the enrollment visit
- 5) Adequate circulatory status, as evidenced by any of the following (for target wound located below the knee):
  - a. Ankle Brachial Index (ABI)  $\geq 0.7$  -  $\leq 1.20$
  - b. If ABI non-compressible (ABI  $> 1.2$ ), then toe brachial Index (TBI)  $> 0.5$
  - c. SPP  $> 30 \text{ mmHg}$
  - d. TcOM  $> 30 \text{ mmHg}$
- 6) At least 4 weeks since revascularization procedure, if one has been performed
- 7) Able to complete Topical Oxygen Therapy 4 days/week for 16 weeks (must be able to remove existing wound dressing and apply TO2 Boot/ treatment, and then re-dress wound)

#### **Exclusion Criteria:**

- 1) Ulcer in area of radiation treatment.
- 2) Active malignancy at site of ulcer
- 3) Current treatment with wound VAC or weekly compression dressings
- 4) Untreated infection at site of ulcer (i.e. cellulitis or osteomyelitis)
  - a. If acute osteomyelitis has been diagnosed, patient may be enrolled only after the infection has been controlled. Including:
    1. Debridement of infected bone if necessary
    2. Patient has received at least 2 weeks of appropriate antibiotics
- 5) ABI  $< 0.7$  or  $> 1.2$

#### **Study Procedure:**

**Note:** As much as possible, study visits will be completed at the Indiana University Health Comprehensive Wound Center (CWC). However, due to the patient population, visits at the CWC are not always possible. For those who are unable to obtain transportation for research visits, approved research personnel will conduct these visits at the subject's home; the need for home visits will be assessed on a case-by-case basis. Study visits completed at the subject's home will include all of the same visit activities; subjects will be instructed that research personnel cannot perform any other health care services at these visits.

